### **Rationale for Inclusion Criteria**

- |        |  |
|--------|--|
| 1 – 8  | To select the appropriate subject population   |
| 9 – 11 | Upadacitinib is teratogenic in both rats and rabbits. The effect of upadacitinib on human pregnancy and reproduction is unknown. |
| 12     | In accordance with harmonized Good Clinical Practice (GCP)   |

### **5.2.2 Exclusion Criteria**

1. Intolerant to MTX.
2. Prior exposure to any JAK inhibitor (including but not limited to tofacitinib, baricitinib, and filgotinib).
3. Prior exposure to any bDMARD(s).
4. History of any arthritis with onset prior to age 17 years or current diagnosis of inflammatory joint disease other than RA (including but not limited to gout, systemic lupus erythematosus, psoriatic arthritis, axial spondyloarthritis including ankylosing spondylitis and non-radiographic axial spondyloarthritis, reactive arthritis, overlap connective tissue diseases, scleroderma, polymyositis,

dermatomyositis, fibromyalgia [currently with active symptoms]). Current diagnosis of secondary Sjogren's Syndrome is permitted.

5. Has been treated with intra-articular, intramuscular, intravenous, trigger point or tender point, intra-bursa, or intra-tendon sheath corticosteroids in the preceding 8 weeks prior to the first dose of study drug.
6. Has been treated with any investigational drug within 30 days or five half-lives of the drug (whichever is longer) prior to the first dose of study drug or is currently enrolled in another clinical study.
7. Female who is pregnant, breastfeeding or considering becoming pregnant during the study or for approximately 180 days after the last dose of study drug.
8. Male subject who is considering fathering a child or donating sperm during the study or for approximately 180 days after the last dose of study drug.
9. Any active or recurrent viral infection that, based on the Investigator's clinical assessment, makes the subject an unsuitable candidate for the study, including hepatitis B virus (HBV) or hepatitis C virus (HCV), recurrent or disseminated (even a single episode) herpes zoster, disseminated (even a single episode) herpes simplex, or known history of human immunodeficiency virus (HIV). Active HBV and HCV are defined as:
  - HBV: hepatitis B surface antigen (HBs Ag) positive (+) or detected sensitivity on the HBV deoxyribonucleic acid (DNA) polymerase chain reaction (PCR) qualitative test for Hepatitis B core antibody (HBc Ab) positive (+) subjects; (and for Hepatitis B surface antibody positive [+] subjects in Japan only);
  - HCV: HCV ribonucleic acid (RNA) detectable in any subject with anti-HCV antibody (HCV Ab).
10. Subject has active TB or meets TB exclusionary parameters (refer to Section 5.3.1.1 for specific requirements for TB testing).

11. Systemic use of known strong cytochrome P450 3A (CYP3A) inhibitors or strong CYP3A inducers from Screening through the end of the study (refer to [Table 1](#) for examples of commonly used strong CYP3A inhibitors and inducers).
12. Receipt of any live vaccine within 4 weeks prior to the first dose of study drug, or expected need of live vaccination during study participation including at least 4 weeks after the last dose of study drug.
13. History of any malignancy except for successfully treated NMSC or localized carcinoma in situ of the cervix.
14. History of clinically significant (per Investigator's judgment) drug or alcohol abuse within the last 6 months.
15. History of gastrointestinal perforation (other than appendicitis or penetrating injury), diverticulitis, or significantly increased risk for GI perforation per investigator judgment.
16. Conditions that could interfere with drug absorption including but not limited to short bowel syndrome.
17. Subject has been a previous recipient of an organ transplant.
18. History of clinically significant medical conditions or any other reason that in the opinion of the Investigator would interfere with the subject's participation in this study or would make the subject an unsuitable candidate to receive study drug.
19. Active infection(s) requiring treatment with parenteral anti-infectives within 30 days, or oral anti-infectives within 14 days prior the first dose of study drug.
20. History of an allergic reaction or significant sensitivity to constituents of the study drug(s) (and their excipients) and/or other products in the same class.
21. Laboratory values meeting the following criteria within the Screening period prior to the first dose of study drug:
  - Serum aspartate transaminase (AST)  $> 2 \times$  ULN
  - Serum alanine transaminase (ALT)  $> 2 \times$  ULN

- Estimated glomerular filtration rate (GFR) by simplified 4-variable Modification of Diet in Renal Disease (MDRD) formula  $< 40 \text{ mL/min/1.73 m}^2$
  - Total white blood cell count (WBC)  $< 2,500/\mu\text{L}$
  - Absolute neutrophil count (ANC)  $< 1,500/\mu\text{L}$
  - Platelet count  $< 100,000/\mu\text{L}$
  - Absolute lymphocyte count  $< 800/\mu\text{L}$
  - Hemoglobin  $< 10 \text{ g/dL}$
22. History of any of the following cardiovascular conditions:
- Moderate to severe congestive heart failure (New York Heart Association class III or IV),
  - Recent (within past 6 months) cerebrovascular accident, myocardial infarction, coronary stenting;
  - Uncontrolled hypertension as defined by a persistent, confirmed systolic blood pressure (BP)  $> 160 \text{ mmHg}$  or diastolic BP  $> 100 \text{ mmHg}$ .
  - Any other condition which, in the opinion of the Investigator, would put the subject at risk by participating in the protocol.
23. Clinically relevant or significant ECG abnormalities, including ECG with QT interval corrected for heart rate (QTc) using Fridericia's correction formula (QTcF)  $> 500 \text{ msec}$ .
24. For subjects in Japan only: Positive result of beta-D-glucan (screening for pneumocystis jiroveci infection).

### **Rationale for Exclusion Criteria**

- |               |  |
|---------------|--|
| 1 – 2         | To select the appropriate subject population   |
| 7 – 8         | Upadacitinib is teratogenic in both rats and rabbits. The effect of upadacitinib on human pregnancy and reproduction is unknown. |
| 3 – 6, 9 – 24 | To ensure safety of the subjects throughout the study  |

### **5.2.3 Prior, Concomitant, and Prohibited Therapy**

Any medication or vaccine (including over-the-counter or prescription medicines, vitamins and/or herbal supplements including folic acid) that the subject is receiving within 28 days prior to Screening, or receives during the study, must be recorded along with the reason for use, date(s) of administration including start and end dates, and dosage information including dose, route and frequency on the appropriate electronic case report form (eCRF). Also, medications including but not limited to DMARDs taken for RA (based on subject recollection and available medical records), should be entered into the appropriate eCRF.

The AbbVie Therapeutic Area Medical Director should be contacted if there are any questions regarding concomitant or prior therapies.

#### **5.2.3.1 Permitted Background RA Therapy**

Subjects should continue on their stable doses of NSAIDs, acetaminophen/paracetamol, oral corticosteroids (equivalent to prednisone  $\leq$  10 mg/day), or inhaled corticosteroids.

- If taking any of the above on a scheduled basis, they should continue to take them as they did at study entry with no change in dose or frequency, including on study visit days.
- If not taking any of the above at baseline, these must not be initiated except where permitted by protocol-defined rescue therapy.
- If taking any of the above, including low potency analgesics, i.e., tramadol, codeine, hydrocodone, or propoxyphene at baseline on an as-needed basis (PRN), they should continue to use them for the same reason and same dose each time but they should not be taken within the 24 hours prior to any study visit to avoid bias in outcome measurements.

In the event of tolerability (or other safety) issues, the doses of these medications may be decreased or discontinued with substitution of another permitted medication from that class (see Section 5.2.3.2 for prohibited therapies). PRN use of inhaled corticosteroids is permitted at any time.

In Period 1, starting at Week 26 (after Week 26 assessments have been performed) and thereafter, intra-articular, intramuscular, intravenous, trigger point or tender point, intra-bursa, and intra-tendon sheath injections of corticosteroids, dosage and frequency per standard of care, are allowed. To avoid confounding effects of systemic absorption of intra-articular corticosteroids, joint injections should be avoided, if possible, within 21 days prior to the next scheduled study visit. For the analysis of the TJC and SJC, injected joints will be considered "not assessable" for 3 months from the time of the intra-articular injection. Refer to Section 5.2.3.3 for rescue therapy at Week 26.

In Period 2, starting at Week 48 (after Week 48 assessments have been performed) and thereafter, initiation of or change in corticosteroids (including: oral, intra-articular, trigger point or tender point, intra-bursa, intra-tendon sheath, intramuscular and intravenous) is allowed. In addition, the initiation of or change in NSAIDs, acetaminophen/paracetamol and low potency narcotics is also permitted to optimize concomitant RA medications. Adding one of the following, sulfasalazine, hydroxychloroquine, or chloroquine, is also permitted, as per local label. Period 2 may be unblinded after all subjects complete Period 1, at which time the Investigator will know if the subject is taking MTX or MTX placebo. If subject is not taking MTX, he/she may add a maximum of 2 csDMARDs, including MTX, leflunomide, sulfasalazine, hydroxychloroquine, or chloroquine, but not MTX plus leflunomide. For RA flare treatment, no more than 3 consecutive days of high-dose systemic corticosteroids (maximum dose of 0.5 mg/kg/day of prednisone or its equivalent) are allowed, after which subject should resume his/her usual daily oral corticosteroid dose.

### **Traditional Chinese Medicine**

Traditional oral Chinese medicine cannot be initiated or changed during the study as these may interfere with upadacitinib metabolism and exposure and may impact efficacy and safety of upadacitinib treatment.

### **5.2.3.2 Prohibited Therapy**

Local label recommendations for contraindicated concomitant therapies with MTX (i.e., trimethoprim-sulfamethoxazole) should be followed.

#### **JAK Inhibitor**

Prior exposure to JAK inhibitors and concurrent use during the study (including but not limited to tofacitinib [Xeljanz®], baricitinib, and filgotinib) is not allowed.

#### **Corticosteroids**

Oral corticosteroids > 10 mg prednisone/day, or equivalent, are NOT allowed in Period 1. Intra-articular, intramuscular, intravenous, trigger point or tender point, intra-bursa, and intra-tendon sheath corticosteroids are NOT allowed up to Week 26. There are exceptions if rescue therapy is needed between Weeks 12 and 24. Refer to Section [5.2.3.3](#).

#### **Biologic Therapies**

All biologic therapies are prohibited during the study (i.e., Periods 1 and 2).

Subjects with prior exposure to bDMARDs are excluded from participation in this study.

Examples of biologic therapies include but are not limited to the following:

- Humira® (adalimumab)
- Enbrel® (etanercept)
- Remicade® (infliximab)
- Orencia® (abatacept)
- Kineret® (anakinra)
- Rituxan® (rituximab)
- Cimzia® (certolizumab pegol)
- Simponi® (golimumab)
- Actemra® (tocilizumab)

- Raptiva® (efalizumab)
- Tysabri® (natalizumab)
- Stelara® (ustekinumab)
- Benlysta® (belimumab)
- Dupixent® (dupilumab)
- Taltz® (ixekizumab)
- Cosentyx® (secukinumab)
- Entyvio® (vedolizumab)

### **csDMARD Therapies**

Subjects must be naïve to MTX; however, those who have received not more than 3 weekly doses of MTX may be enrolled if they complete a 4-week washout of the MTX before the first dose of study drug (Inclusion Criterion 3, Section 5.2.1).

Subjects must have discontinued all csDMARDs prior to Baseline Visit as specified in the washout procedures (Inclusion Criterion 4, Section 5.2.1).

### **Strong CYP3A Inhibitors or Inducers**

Systemic use of known strong CYP3A inhibitors or strong CYP3A inducers is excluded from the Screening Visit through the end of the study (i.e., Periods 1 and 2). The most common strong CYP3A inhibitors and inducers are listed in Table 1.

**Table 1. Examples of Commonly Used Strong CYP3A Inhibitors and Inducers**

Strong CYP3A Inhibitors	Strong CYP3A Inducers
Boceprevir Cobicistat Clarithromycin Conivaptan Grapefruit (fruit or juice) Indinavir Itraconazole Ketoconazole Lopinavir/Ritonavir Mibefradil Nefazodone Nelfinavir Posaconazole Ritonavir Saquinavir Telaprevir Telithromycin Troleandomycin Voriconazole	Avasimibe Carbamazepine Phenytoin Rifampin Rifapentine St. John's Wort

In Period 2, when study drug has been unblinded, systemic use of known strong CYP3A inhibitors or strong CYP3A inducers is permitted for subjects not receiving upadacitinib.

### **Opiates**

High potency opiates are not permitted during the study (i.e., Periods 1 and 2), with the exception of analgesic care related to AEs or SAEs and subjects must have discontinued high potency opiates at least 1 week prior to the first dose of study drug, including (but not limited to):

- oxycodone
- oxymorphone
- fentanyl
- levorphanol
- buprenorphine

- methadone
- hydromorphone
- morphine
- meperidine

### **Investigational Drugs**

Subjects who have been treated with any investigational drug within 30 days or five half-lives of the drug (whichever is longer) prior to the first dose of study drug are excluded from participation in this study. Investigational drugs are also prohibited during the study.

### **Vaccines**

Although not mandated by the protocol, vaccines recommended by local guidelines should be considered. If the subject and investigator choose to administer live vaccines, these vaccinations must be completed (per local label) 4 weeks before first dose of study drug with appropriate precautions. Live vaccinations are prohibited during Period 1, including at least 30 days (or longer if required locally) after last dose of study drug.

Examples of live vaccines include, but are not limited to, the following:

- Monovalent live influenza A (H1N1) (intranasal);
- Seasonal trivalent live influenza (intranasal);
- Zostavax (herpes zoster, live attenuated);
- Rotavirus;
- Varicella (chicken pox);
- Measles-mumps-rubella or measles mumps rubella varicella;
- Oral polio vaccine;
- Smallpox;
- Yellow fever;
- Bacille Calmette-Guérin (BCG);

- Typhoid.

In Period 2, if a live vaccine must be administered during study participation, study drug must be held for at least 30 days prior to the vaccination and at least 30 days after the vaccination (or longer if required locally).

If the live herpes zoster vaccine is to be administered and there is no known history of primary varicella (chicken pox), preexisting immunity to varicella should be confirmed with antibody testing prior to administration of the herpes zoster vaccine. If varicella antibody testing is negative, the live herpes zoster vaccine should not be administered.

Administration of inactivated (non-live) vaccines is permitted during the study according to local practice guidelines. Examples of common vaccines that are inactivated, toxoid or biosynthetic, include but are not limited to: injectable influenza vaccine, pneumococcal, Shingrix (zoster vaccine, recombinant, adjuvanted) and, pertussis (Tdap) vaccines.

If the nasal Influenza vaccine is administered, the vaccine must be administered at least 4 weeks prior to first dose of study drug.

### **5.2.3.3 Rescue Therapy**

Rescue therapy for those subjects who meet the following criteria from Week 12 through Week 24 are as follows:

- Those who do not achieve  $\geq 20\%$  improvement in both TJC and SJC compared with baseline at two consecutive visits starting at Week 12 will continue on their blinded therapy and the Investigator should optimize (initiate or increase) background RA medications: NSAIDs, corticosteroids (oral  $\leq 10$  mg/day prednisone equivalent or prednisone equivalent  $\leq 0.5$  mg/kg/day for 3 consecutive days) and/or low-potency analgesics.

Rescue therapy for those subjects who meet the following criteria at Week 26 are as follows:

1. Subjects who were originally randomized to MTX:
  - Those who do not achieve CR by CDAI:
    - but achieve  $\geq 20\%$  improvement in both TJC and SJC compared with baseline will continue on blinded MTX and the Investigator should optimize (initiate or increase) background RA medications: NSAIDs, corticosteroids (oral  $\leq 10$  mg/day prednisone equivalent and up to 2 local injections), low-potency analgesics and csDMARDs (only 1 of the following: sulfasalazine, hydroxychloroquine or chloroquine) throughout the remainder of Period 1 and until the study is unblinded.
    - and do not achieve  $\geq 20\%$  improvement in both TJC and SJC compared with baseline will be re-randomized in a 1:1 ratio to receive blinded upadacitinib 15 mg QD or upadacitinib 30 mg QD (for subjects in Japan: randomize 1:1:1 to receive upadacitinib 7.5 mg QD, 15 mg QD, or 30 mg QD) while continuing MTX treatment in a blinded manner and will remain on upadacitinib plus MTX throughout the remainder of Period 1 and until the study is unblinded.
  - Those who achieve Clinical Remission (CR) by CDAI ( $CDAI \leq 2.8$ ) at Week 26 will continue blinded treatment with MTX throughout the remainder of Period 1 and until the study is unblinded (the study is unblinded when all subjects have completed Period 1).
2. Subjects who were originally randomized to upadacitinib:
  - Those who do not achieve CR by CDAI:
    - but achieve  $\geq 20\%$  improvement in both TJC and SJC compared with baseline will continue on blinded upadacitinib and the Investigator should optimize (initiate or increase the dose) background RA medications: NSAIDs, corticosteroids (oral  $\leq 10$  mg/day prednisone equivalent and up to 2 local injections), low potency analgesics and csDMARDs (only 1 of the following: sulfasalazine, hydroxychloroquine or chloroquine) throughout the remainder of Period 1 and until the study is unblinded.
    - but do not achieve  $\geq 20\%$  improvement in both TJC and SJC compared with baseline will add MTX 10 mg/week (7.5 mg for Japan) to upadacitinib in a blinded manner and will remain on upadacitinib plus

MTX 10 mg/week (7.5 mg for Japan) throughout the remainder of Period 1 and until the study is unblinded.

- Those who achieve CR by CDAI ( $CDAI \leq 2.8$ ) at Week 26 will continue blinded treatment with upadacitinib throughout the remainder of Period 1 and until the study is unblinded (the study is unblinded when all subjects have completed Period 1).

Rescue therapy for those subjects who meet the following criteria from Week 36 through Week 40 are as follows:

- Those who do not achieve  $\geq 20\%$  improvement in both TJC and SJC compared with baseline at two consecutive visits starting at Week 36 will be rescued with optimizing (initiate or increase) background RA medications: NSAIDs, corticosteroids (oral  $\leq 10$  mg/day prednisone equivalent or prednisone equivalent  $\leq 0.5$  mg/kg/day for 3 consecutive days and up to 2 local injections), low-potency analgesics and csDMARDs (only 1 of the following: sulfasalazine, hydroxychloroquine or chloroquine).

## 5.2.4 Contraception Recommendations

### Contraception Recommendation for Females

A woman who is postmenopausal or permanently surgically sterile (bilateral oophorectomy, bilateral salpingectomy or hysterectomy) is not considered to be a woman of childbearing potential and is not required to follow contraception recommendations.

Postmenopausal is defined as:

- Age  $\geq 55$  years with no menses for 12 or more months without an alternative medical cause; or
- Age  $< 55$  years with no menses for 12 or more months without an alternative medical cause AND an FSH level  $> 40$  mIU/mL.

If the female subject is < 55 years of age:

AND has had no menses for  $\geq 12$  months AND has no history of permanent surgical sterilization (defined above), FSH should be tested at Screening.

- If FSH is not tested, it is assumed that the subject is of childbearing potential and protocol-specified contraception is required.
- If the FSH is tested and the result is consistent with post-menopausal status, contraception is not required.
- If the FSH is tested and the result is consistent with pre-menopausal status, contraception is required and a serum pregnancy test must be performed (see Section 5.3.1.1 pregnancy test).

For a female subject at any age:

- Female subjects with menses within the past 12 months are of childbearing potential and FSH is therefore not required but contraception is required.
- Female subjects who are surgically sterile (defined above) are not of childbearing potential and therefore no FSH testing or contraception is required.

A woman who does not meet the definition of postmenopausal or permanently surgically sterile is considered of childbearing potential and is required to practice at least one of the following highly effective methods of birth control that is effective from Study Day 1 (or earlier) through at least 180 days after the last dose of study drug.

- Combined (estrogen and progestogen containing) hormonal contraception (oral, intravaginal, transdermal, injectable) associated with the inhibition of ovulation, initiated at least 30 days prior to Study Day 1.
- Progestogen-only hormonal contraception (oral, injectable, implantable) associated with inhibition of ovulation, initiated at least 30 days prior to Study Day 1.
- Bilateral tubal occlusion/ligation.

- Vasectomized partner(s), provided the vasectomized partner has received medical confirmation of the surgical success and is the sole sexual partner of the women of childbearing potential trial participant.
- Intrauterine device (IUD).
- Intrauterine hormone-releasing system (IUS).
- True abstinence (if acceptable per local requirements): Refraining from heterosexual intercourse when this is in line with the preferred and usual lifestyle of the subject (periodic abstinence [e.g., calendar, ovulation, symptothermal, post-ovulation methods] and withdrawal are not acceptable).

If required per local practices, male or female condom with or without spermicide OR cap, diaphragm or sponge with spermicide should be used in addition to one of the highly effective birth control methods listed above (excluding true abstinence).

It is important to note that contraception recommendations described above are specifically intended to prevent pregnancy during and after exposure to the investigational therapies, upadacitinib and MTX. In Period 2, starting at Week 48, concomitant csDMARDs (i.e., sulfasalazine, hydroxychloroquine, chloroquine and leflunomide) can be prescribed, per standard of care. The duration of contraception after discontinuation of these prescribed csDMARDs should be based on the local label.

If during the course of the study a woman becomes surgically sterile or post-menopausal and complete documentation is available, contraception measures as defined above are no longer required.

Additional local requirements may apply. Refer to [Appendix C](#) for local requirements (Canada and Colombia).

### **Contraception Recommendation for Males**

There are no contraception requirements for male subjects receiving upadacitinib only, or their female partner(s).

For a male subject receiving MTX who has a female partner who is postmenopausal or permanently sterile, no contraception is required.

A male subject receiving MTX who is sexually active with female partner(s) of childbearing potential must agree from Study Day 1 through 180 days after the last dose of MTX study drug to practice contraception with:

- Condom use and female partner(s) using at least one of the contraceptive measures (as defined in the protocol for female study subjects of childbearing potential).
- True abstinence: Refraining from heterosexual intercourse-when this is in line with the preferred and usual lifestyle of the subject. (Note: Periodic abstinence [e.g., calendar, ovulation, symptothermal, post-ovulation methods] and withdrawal are not acceptable).

Additionally, male subjects receiving MTX must agree not to donate sperm from Study Day 1 through 180 days after the last dose of MTX study drug.

Male subjects receiving MTX are responsible for informing his partner(s) of the risk of becoming pregnant and for reporting any pregnancy to the study doctor.

It is important to note that contraception and sperm donation recommendations described above are specifically intended to prevent pregnancy during and after exposure to the investigational therapy, MTX. In Period 2, starting at Week 48, concomitant csDMARDs (i.e., sulfasalazine, hydroxychloroquine, chloroquine and leflunomide) can be prescribed, per standard of care. The duration of contraception and requirement not to donate sperm after discontinuation of these prescribed csDMARDs should be based on the local label.

Additional local requirements may apply. Refer to [Appendix C](#) for local requirements (Canada and Colombia).

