  10. If female, subject must be postmenopausal, OR permanently surgically sterile, OR for women of childbearing potential practicing at least one protocol-specified method of birth control (refer to Section 5.2.4), that is effective from Study Day 1 through at least 180 days after the last dose of study drug.
-

- Additional local requirements may apply. Refer to [Appendix C](#) for local requirements.
11. Male subjects who are sexually active with female partner(s) of childbearing potential must agree from Study Day 1 through 180 days after the last dose of study drug to practice the protocol-specified contraception (refer to Section [5.2.4](#)).
- Additional local requirements may apply. Refer to [Appendix C](#) for local requirements.
12. Subjects must voluntarily sign and date an informed consent, approved by an Independent Ethics Committee (IEC)/Institutional Review Board (IRB), prior to the initiation of any screening or study-specific procedures.

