In the event a urine pregnancy test may not be performed at the protocol specified visits due to study modifications related to a state of emergency or pandemic situation like COVID-19, it can be performed by subjects at a local laboratory or it is possible for the Investigator to arrange a shipment from the study site directly to the subject's home of

urine pregnancy test kits to have the urine pregnancy test done at home (see Section 5.3.1.1 - Sub-Section "Study Drug Dispensing, Dosing, and Compliance" for details). Home urine pregnancy test should be performed monthly, regardless of ability to obtain other laboratory samples.

At each visit, the study staff should review the pregnancy avoidance recommendations with each subject of childbearing potential and male subjects receiving MTX with a partner of childbearing potential, and document this discussion in the subject's source records.

If during the course of the study a woman becomes surgically sterile or post-menopausal and complete documentation as described in Section 5.2.4 is available, pregnancy testing is no longer required.

A pregnant or breastfeeding female will not be eligible for participation in this study or be allowed to continue study drug.

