## **5.5.5 Blinding**

### **5.5.5.1 Blinding of Investigational Product**

All AbbVie personnel with direct oversight conduct and management of the trial (with the exception of AbbVie Drug Supply Management Team), the Investigator, study site personnel, and the subject will remain blinded to each subject's treatment throughout Period 1.

In order to maintain the blind, the upadacitinib and placebo tablets along with MTX and placebo capsules provided for the study will be identical in appearance. The IRT will provide access to unblinded subject treatment information in the case of medical emergency.

In the event of a medical situation that requires unblinding of the study drug assignment, the Investigator is requested to contact the AbbVie Therapeutic Area Medical Director prior to breaking the blind. However, if an urgent therapeutic intervention is necessary which warrants breaking the blind prior to contacting the AbbVie Therapeutic Area Medical Director, the Investigator can directly access the IRT system to break the blind without AbbVie notification or agreement. Unblinding is available in the IRT system via the Unblind Subject transaction, which is available only to the Investigator. If the IRT system is unavailable, unblinding may occur by contacting EndPoint technical support via either phone (preferred) or email ([[contact]](mailto:[contact])). For country-specific phone numbers, please see the following website: <http://www.endpointclinical.com/help-desk/>. In the event that the blind is broken before notification to the AbbVie Therapeutic Area Medical Director, we request that the AbbVie Therapeutic Area Medical Director be notified within 24 hours of the blind being broken. The date and reason that the blind was broken must be conveyed to AbbVie and recorded on the appropriate eCRF.

When the last subject completes the last visit of Period 1 (Week 48), study drug assignment in both periods may be unblinded to the Sponsor and sites, and subjects would then be dispensed study drug in an open-label fashion until the completion of Period 2.

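### The protocol's male contraception and sperm-donation rules name different men and different end dates, and the end date is still unsettled for some men in Period 2

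*Protocol*

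**What the plan says.** Two eligibility criteria address men without reference to treatment arm. Inclusion 11 in Protocol Section 5.2.1 reads "Male subjects who are sexually active with female partner(s) of childbearing potential must agree from Study Day 1 through 180 days after the last dose"; the clock is set by any study drug, and the criterion points to Section 5.2.4 for the method. Exclusion 8 in Section 5.2.2 bars a "Male subject who is considering fathering a child or donating sperm during the study or for approximately 180 days after the last dose"; its clock is likewise set by any study drug, and it has no pointer to 5.2.4. The rationale tables in 5.2.1 and 5.2.2 justify both criteria by upadacitinib's teratogenicity in animals.

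The male part of Section 5.2.4 takes a different line: "There are no contraception requirements for male subjects receiving upadacitinib only, or their female partner(s". Contraception and the sperm-donation ban apply only to men receiving MTX, and both end 180 days after the last MTX study drug. The section describes the purpose as preventing pregnancy around exposure to MTX as investigational therapy. Appendix C has the same split for Canada and Colombia: inclusion 11 without an arm condition, then male recommendations that depend on MTX.

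Section 5.3.1.1 (Pregnancy Test) has staff counsel, at each visit, "male subjects receiving MTX with a partner of childbearing potential". Section 6.1.6 also conditions on MTX for men, but its 180 days run from the last study drug administration.

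On blinding, Section 5.5.5.1 says that "the Investigator, study site personnel, and the subject will remain blinded to each subject's treatment throughout Period 1". On Period 2, Section 5.2.3.1 says that after unblinding: "If subject is not taking MTX, he/she may add a maximum of 2 csDMARDs, including MTX, leflunomide, sulfasalazine, hydroxychloroquine, or chloroquine", though not MTX together with leflunomide.

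**The concern.** These are reproductive-safety instructions that a site must turn into advice for an individual man. As written, the criteria under which he entered and the section they cite can give him different answers on whether a rule applies and when it ends. The rationale makes the conflict plainer: the criteria rest on upadacitinib, while 5.2.4 exempts men on upadacitinib only from contraception and rests on MTX.

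A second difficulty is practical. A rule that depends on receiving MTX needs someone at the site to know who receives it. During the blinded phase nobody there did.

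**Working it through.** No power, alpha or sample-size figure is involved. The check sets the passages side by side and follows the 180-day clock.

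| Place | Men addressed | End of period |
|---|---|---|
| Inclusion 11 (5.2.1 and Appendix C) | Sexually active with a partner of childbearing potential; any arm | 180 days after last study drug |
| Exclusion 8 (5.2.2) | Any man considering fathering a child or donating sperm; any arm | About 180 days after last study drug |
| 5.2.4, males (and Appendix C) | Only men receiving MTX; no contraception requirement on upadacitinib only | 180 days after last MTX study drug |
| 5.3.1.1, Pregnancy Test | Men receiving MTX with a partner of childbearing potential | Counselling at each visit; none stated |
| 6.1.6 | Only men receiving MTX | 180 days after last study drug |

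Let U be the day of the last upadacitinib dose, M the last dose of MTX study drug and B the last dose of background MTX.

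1. *MTX study drug only.* M is also the last study drug, so every passage that states an end gives M + 180. The text is consistent here.
2. *Upadacitinib only.* Exclusion 8, and inclusion 11 on its face, give U + 180. Section 5.2.4 sets no period.
3. *Both as study drug, MTX stopped first (M < U).* Inclusion 11, exclusion 8 and 6.1.6 give U + 180; 5.2.4 gives M + 180. The difference is (U + 180) − (M + 180) = U − M. Section 5.5.4 allows the two drugs to be interrupted separately once Period 2 is unblinded, which for any subject is no earlier than his Week 48. Treatment ends by Week 260. The outer bound on the difference is therefore 260 − 48 = 212 weeks; it may be far smaller.
4. *Upadacitinib as study drug, background MTX added in Period 2.* There is no M, so the 5.2.4 clock has no start. The local-label sentence in 5.2.4 gives a closed list of four csDMARDs, and MTX is not among them. Inclusion 11, exclusion 8 and 6.1.6 count from U. No passage counts from B.

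*Blinded phase.* Site and subject were blinded throughout Period 1, and Period 2 stayed blinded until the last subject completed Week 48. Section 5.1 adds MTX to upadacitinib at Week 26, in blinded form, for some inadequate responders. A man could therefore become an MTX recipient without anyone at the site knowing, while 5.2.4 dates his obligation from Study Day 1. Section 5.2.3.1 confirms that the investigator learns MTX status at unblinding. Neither 5.2.4 nor the visit counselling in 5.3.1.1 could be applied by actual MTX receipt in that phase.

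**The case against.** The strongest reply is timing. The protocol synopsis is dated 03 December 2020. Section 5.5.5.2 records that all subjects had reached the end of Period 1 by September 2018, and from Amendment 6 upadacitinib 15 mg and 30 mg and MTX are given open-label. SAP Section 11.1 and Appendix B say that the primary analysis and Period 1 reporting are complete. A reader might infer that sites are now enrolling or advising blinded men wrongly, or breaking the blind to give advice and so threatening the primary endpoints. The documents do not support that. They also do not show what 5.2.4 said under the amendments in force while subjects were blinded. And a site could have applied inclusion 11 and exclusion 8 without knowing the assignment. This reply stands and makes the blinding point largely historical.

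Second, inclusion 11 does not bind every man. It covers those sexually active with a partner of childbearing potential, and because it cites 5.2.4 its content can be read as whatever 5.2.4 requires. That is fair, but its clock still names study drug where 5.2.4 names MTX study drug. Exclusion 8 is a test of intention rather than a contraception rule, but it has no link to 5.2.4 and no arm condition.

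Third, a reader might infer that background MTX is not covered at all. That goes too far. A man who adds it is receiving MTX and is no longer on upadacitinib only, so the requirement during use can be read as applying, although the stated scope (investigational MTX) leaves some doubt. Section 5.1 allows Period 2 background drugs according to local label. What is missing is an end date for contraception and sperm donation counted from the last background MTX dose.

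**Conclusion.** The contradiction is real and can be verified on the page. Inclusion 11, exclusion 8 and their rationales do not agree with 5.2.4 and the male text of Appendix C on which men are covered or on the dose that starts the 180 days. Section 6.1.6 agrees with 5.2.4 on the men and with the criteria on the clock.

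Three situations remain open in Period 2. For a man on upadacitinib only, exclusion 8 sets a period and 5.2.4 does not. A man on both drugs who stops MTX first has two end dates that differ by U − M. A man who adds background MTX has no end date tied to that drug. The second situation assumes that a separate interruption of MTX can become permanent while upadacitinib continues; Section 5.5.4 permits separate interruption but does not spell out that outcome.

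No count of affected men is offered. The documents give neither the proportion of men nor the number taking both drugs or background MTX. Nothing here touches the completed efficacy analyses. No view is taken on which rule is clinically right for either drug.

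**What to change.** Reconcile inclusion 11, exclusion 8, the two rationale tables, 5.2.4, 5.3.1.1, 6.1.6 and Appendix C so that they name the same men and the same reference dose for the end of the period. State in 5.2.4 which end date governs MTX taken as a background csDMARD in Period 2. Any rule kept for a blinded phase should be one that a site can apply without knowing the assignment; by-treatment wording belongs after unblinding. The sponsor decides the content of the rule.

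The cost is protocol wording and a matching sentence in the consent form. No new procedure, visit or analysis is needed.
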